2.1.4 Safety endpoints

The safety analysis will be based on the reported adverse events (AE) and other safety information, such as clinical laboratory data, vital signs, physical examination, electrocardiogram (ECG), etc.

Observation period

The observation period will be divided into 4 epochs:

- The **screening** epoch is defined as the time from the signed informed consent date up to the first administration of the IMP.
- The **treatment** epoch is defined as the time from the first administration of the IMP to the last administration of the IMP + 14 days or until the patient enters the extension study.
- The **residual treatment** epoch is defined as the time from the last administration of the IMP + 15 days to the last administration of the IMP + 98 days or until the patient enters the extension study.

The treatment-emergent adverse event (TEAE) period will include both **treatment** and **residual treatment** epochs.

• The **posttreatment** epoch is defined as the period of time starting the day after the end of the treatment-emergent adverse event period up to the end of the study (defined as last protocol-planned visit or lost to follow-up or the resolution/stabilization of all serious adverse events and adverse events with prespecified monitoring).

The on-study observation period is defined as the time from start of treatment until the end of the study.

2.1.4.1 Adverse events variables

Adverse event observation period

- Pretreatment adverse events are adverse events that developed or worsened or became serious from the signed informed consent date up to first administration of IMP.
- Treatment-emergent adverse events are adverse events that developed or worsened or became serious during the treatment-emergent adverse event epoch.
- Posttreatment adverse events are adverse events that developed or worsened or became serious during the posttreatment epoch.

All adverse events (including serious adverse events and adverse events with prespecified monitoring) will be coded to a lower-level term (LLT), preferred term (PT), high-level term (HLT), high-level group term (HLGT), and associated primary system organ class (SOC) using the version of MedDRA currently in effect at Sanofi at the time of database lock.

Adverse events for each patient will be monitored and documented from the time the subject gives informed consent at Visit 1 until the End-of-Study visit (Visit 14) or till the rollover to the extension study, except for:

- Serious AEs
- Adverse events that are ongoing at database lock

For ongoing AEs at database lock, observations may continue beyond the last planned visit per protocol, and additional investigations may be requested by the monitoring team up to as noticed by the Sponsor. Patients who experience an ongoing SAE or an AESI, at the prespecified study end-date, should be followed until resolution, stabilization, or death and related data will be collected. Any SAE brought to the attention of the Investigator at any time after the end of the study and considered by him/her to be caused by the IMP with a reasonable possibility, should be reported to the monitoring team.

Adverse events of special interests include the following terms:

• Anaphylactic or systemic allergic reactions, that are related to IMP and that require treatment (refer to Appendix H for the definition of anaphylaxis).

- Severe injection site reactions that last longer than 24 hours.
- Any infection meeting at least 1 of the following criteria:
 - Any serious infection (SAE)
 - Requires parenteral (intravenous, intramuscular, subcutaneous) antimicrobial therapy
 - Requires oral antimicrobial therapy for longer than 2 weeks
 - Is a parasitic infection
 - Is an opportunistic infection (Appendix I)

Note: Antimicrobial therapy refers to antibiotic, antiviral, and antifungal agents.

- Significant elevation of alanine aminotransferase (ALT)
 - ALT >5 × upper limit of normal (ULN) in patients with baseline ALT $\leq 2 \times$ ULN; or
 - ALT >8 × ULN if baseline ALT >2 × ULN
- Pregnancy of a female subject entered in a study as well as pregnancy occurring in a female partner of a male subject entered in a study with IMP/noninvestigational medicinal product (NIMP)
 - Pregnancy occurring in a female patient entered in the clinical trial or in a female partner of a male patient entered in the clinical trial. It will be qualified as an SAE only if it fulfills 1 of the seriousness criteria.
 - In the event of pregnancy in a female participant, IMP should be discontinued.
 - Follow-up of the pregnancy in a female participant or in a female partner of a male participant is mandatory until the outcome has been determined.
- Symptomatic overdose (serious or non-serious) with IMP/NIMP
 - An overdose (accidental or intentional) with the IMP is an event suspected by the Investigator or spontaneously notified by the patient and defined as at least twice the intended dose during an interval of less than 11 days. The circumstances (ie, accidental or intentional) should be clearly specified in the verbatim and symptoms, if any, entered on separate AE forms.
 - An overdose (accidental or intentional) with any NIMP is an event suspected by the Investigator or spontaneously notified by the patient and defined as at least twice of the intended dose within the intended therapeutic interval. The circumstances (ie, accidental or intentional) should be clearly specified in the verbatim and symptoms, if any, entered on separate AE forms.

Of note, asymptomatic overdose has to be reported as a standard AE.

AESIs and other selected AE groupings will be searched based on the criteria in Table 5.

Table 5 - Criteria for adverse events of special interest and other selected AE grouping
--

AE Grouping	Criteria
AESI	
Anaphylactic reaction	Anaphylactic reaction algorithmic approach (Introductory Guide for Standardised MedDRA Queries (SMQs) Version 18.1): includes anaphylactic reaction narrow SMQ (20000021) terms; for selection based on occurrence of multiple events, the events must have occurred within 24 hours of each other
Hypersensitivity (medically reviewed)	SMQ hypersensitivity (20000214) narrow search and [AE corrective treatment/therapy='Y' or Action taken with IMP='Drug withdrawn' or Action taken with IMP='Drug interrupted'] followed by blinded medical review (documented process) for selection of relevant systemic hypersensitivity events
Serious injection site reactions or severe injection site reactions that last longer than 24 hours	HLT = 'Injection site reaction' and either with serious status, or with severe status and (AE end date/time - AE start date/time) \ge 24 hours or ongoing
Severe or serious infection	Primary SOC = 'Infections and infestations' and with severe or serious status
Parasitic infection	Infection Type 'Parasitic' checked on eCRF Infection Defined as AESI Complementary Form
Opportunistic infection	Infection Type 'Opportunistic' checked on eCRF Infection Defined as AESI Complementary Form
Drug-related hepatic disorder	Drug-related hepatic disorders-Comprehensive search narrow SMQ (20000006)
Pregnancy	Primary SOC = 'Pregnancy, puerperium and perinatal conditions' or PT in (Aborted pregnancy, False negative pregnancy test, Pregnancy test positive, Pregnancy test urine positive, Ectopic pregnancy termination)
Symptomatic overdose with IMP	Is the event a Symptomatic Overdose with IMP? is answered Yes on AE eCRF.
Symptomatic overdose with NIMP	Is the event a Symptomatic Overdose with NIMP? is answered Yes on AE eCRF
Other selected AE grouping	
Injection site reaction	HLT = 'Injection site reaction'
Malignancy	Sub-SMQ (20000091)– Malignant or unspecified tumors
Suicidal behavior	PT in (Completed suicide, Suicidal ideation, Depression suicidal, Suicidal behavior, Suicide attempt)
Partner pregnancy	PT in (Pregnancy of partner, Miscarriage of partner)
Conjunctivitis (narrow)	PT in (Conjunctivitis, Conjunctivitis allergic, Conjunctivitis bacterial, Conjunctivitis viral, Atopic keratoconjunctivitis)

AE Grouping	Criteria
Conjunctivitis (broad)	PT in (Conjunctivitis, Conjunctivitis allergic, Conjunctivitis bacterial, Conjunctivitis viral, Atopic keratoconjunctivitis, Blepharitis, Dry eye, Eye irritation, Eye pruritus, Lacrimation increased, Eye discharge, Foreign body sensation in eyes, Photophobia, Xerophthalmia, Ocular hyperaemia, Conjunctival hyperaemia)
Hypereosinophilia	HLT = 'Eosinophilic disorders' or PT = 'Eosinophil count increased'

2.1.4.2 Deaths

The deaths observation period are per the observation periods defined above.

- Death on-study: deaths occurring during the on-study observation period
- Death on-treatment: deaths occurring during the treatment-emergent adverse event period
- Death post-study: deaths occurring after the end of the study

2.1.4.3 Laboratory safety variables

Clinical laboratory data consists of blood analysis, including hematology, clinical chemistry, serum immunoglobulins, and urinalysis. Clinical laboratory values after conversion will be analyzed into standard international units and international units will be used in all listings and tables.

Blood samples for clinical laboratories will be taken at Visits 1 (Week -8 to -3), 3 (Week 0), 5 (Week 4), 7 (Week 8), 8 (Week 12), 9 (Week 16), 10 (Week 20), 11 (Week 24), 14 (Week 36), and early termination unless otherwise specified. The laboratory parameters will be classified as follows:

- Hematology
 - **Red blood cells and platelets and coagulation**: hemoglobin, hematocrit, platelet count, total red blood cell count
 - White blood cells: total white blood cell (WBC) count, neutrophils, lymphocytes, monocytes, basophils, eosinophils
- Clinical chemistry
 - **Metabolism:** glucose, hemoglobin A1c (HbA1c), total cholesterol, total protein, albumin, creatine phosphokinase
 - Electrolytes: sodium, potassium, chloride, bicarbonate
 - Renal function: creatinine, blood urea nitrogen, uric acid
 - **Liver function**: ALT, aspartate aminotransferase (AST), alkaline phosphatase, lactate dehydrogenase, total bilirubin (in case of values above the normal range, differentiation in conjugated and non-conjugated bilirubin)

- **Pregnancy test**: A serum pregnancy test (β-human chorionic gonadotrophin) will be performed at Screening (Visit 1, Week -8 to -3) in women of childbearing potential
- **Hepatitis screen** (at Visits 1 [Week -8 to -3] and 10 [Week 20]): hepatitis B surface antigen (HBsAg), hepatitis B Surface antibody (HBsAb), Immunoglobulin M (IgM) and Immunoglobulin G (IgG)/total-hepatitis B core antibody (HBcAb), hepatitis C antibody (HCAb). Patients who are IgG/total-HBcAb positive and HBsAg negative at Visit 1 must undergo HBV DNA testing prior to randomization to determine eligibility. In case of results showing HCVAb positive, HCV RNA testing must be negative prior to randomization.
- **HIV screening** (at Visits 1 [Week -8 to -3] and 10 [Week 20]): anti-HIV-1 and HIV-2 antibodies
- Anti-nuclear antibody (ANA) (at Visits 1 [Week -8 to -3] and 10 [Week 20]). Note: anti-double-stranded DNA antibody will be tested if ANA is positive (≥1:160 titer).

Serum immunoglobulins

- Quantitative immunoassays for total IgG, IgG subclasses 1-4, IgM, and Immunoglobulin A (IgA) at Visits 1 (Week -8 to -3), 3 (Week 0), 8 (Week 12), 11 (Week 24), and 14 (Week 36).

Urine samples will be collected as follows:

- Urine dipstick analysis (at Visits 1 [Week -8 to -3], 3 [Week 0], 8 [Week 12], 11 [Week 24], and 14 [Week 36]): specific gravity, pH, glucose, ketones, blood, protein, nitrate, leukocyte esterase, urobilinogen and bilirubin (by dipstick). If any parameter on the dipstick is abnormal, a urine sample should be sent to the central laboratory for testing. If positive for proteins, microscopic analysis is performed by central laboratory.
- A urine dipstick pregnancy test will be performed at Visit 3 (Week 0) prior to randomization and Visits 5 (Week 4), 7 (Week 8), 8 (Week 12), 9 (Week 16), 10 (Week 20), 11 (Week 24), and 14 (Week 36) prior to investigational product administration

Technical formulas are described in Section 2.5.1.

2.1.4.4 Vital signs variables

Vital signs including blood pressure (mmHg), heart rate (beats per minute), respiratory rate (breaths per minute), body temperature (degrees Celsius) and body weight will be measured at every visit. Height (cm) will be measured at the Screening visit (Visit 1) only.

Vital signs will be measured in the sitting position using the same arm at each visit, and will be measured prior to receiving investigational product at the clinic visits.

2.1.4.5 Electrocardiogram variables

One recording of a standard 12-lead ECG will be performed centrally at Visits 1 (Week -8 to -3), 3 (Week 0), 8 (Week 12), 11 (Week 24), and 14 (Week 36). At the post-randomization visits in which an ECG is scheduled, the ECG will be performed prior to investigational product administration.

All measurements will be made from a single lead: lead II, lead I (if lead II is not possible), or lead V5 (if leads II and I are not possible). A minimum of 3 complexes in an appropriate lead (lead II) will be averaged to determine the PR-interval, QT/QTc-interval, QRS-complex and heart rate will be measured for each ECG.

The ECGs will be manually read at a central lab.

2.1.4.6 Physical examination

Physical examinations will be performed at Visits 1 (Week -8 to -3) and 11 (Week 24). They will include an assessment of general appearance, skin, eyes, ear/nose/throat, heart, chest, abdomen, reflexes, lymph nodes, spine, and extremities. All deviations from normal will be recorded, including those attributable to the patient's disease.

2.1.5 Pharmacokinetic variables

Blood samples of serum functional dupilumab will be collected at Visit 3 (Week 0) as sample before the first dose, at Visits 5 (Week 4), 7 (Week 8), 8 (Week 12), 11 (Week 24) as trough samples prior to IMP dosing at each visit, and at Visit 14 (Week 36) during the follow up period.

2.1.6 Anti-drug antibody variables

Determination of anti-drug antibody (ADA) status will be performed at Visits 3 (Week 0), 8 (Week 12), 11 (Week 24), and 14 (Week 36). The ADA status can be negative or a titer value if it is positive. Samples that are positive in the ADA assay will be further characterized for the presence of anti-dupilumab neutralizing antibodies. Patients who discontinue early from treatment or patients who choose not to participate in the LTS12551 study visit may be asked to return to the clinic to have additional ADA samples collected for analysis based on the overall clinical presentation at that time.

ADA incidence will be classified as the following:

Pre-existing immunoreactivity is defined as:

- An ADA-positive response in the assay at baseline with all post treatment ADA results negative, OR
- An ADA-positive response in the assay at baseline with all post treatment ADA responses less than 4-fold over baseline titer levels.

Treatment-emergent anti-drug antibodies is defined as:

• An ADA-positive response in the assay post first dose, when baseline results are negative or missing.

Treatment-boosted anti-drug antibodies is defined as:

• An ADA-positive response in the assay post first dose that is greater than or equal to 4-fold over baseline titer levels, when baseline results are positive.

Treatment-emergent (TE) ADA responses are further classified as transient, persistent or indeterminate

- Persistent response is defined as a treatment-emergent response with 2 or more consecutive ADA-positive sampling time points separated by more than a 12-week period (84 days), with no ADA negative samples in between.
- Indeterminate response is defined as a treatment-emergent response with only the last collected sample positive in the ADA assay.
- Transient response is defined as a treatment-emergent response that is not considered persistent OR indeterminate.

Titer values (titer value category)

- Low (titer <1000)
- Moderate $(1000 \le \text{titer} \le 10000)$
- High (titer >10000)

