OCS Optimization Phase ^a		R N D ^b	N Induction Phase			OCS Reduction Phase								Maintenance Phase				
Week	-8 to -3	-7 to -2	0	2	4	6	8	10 ^C	12	14 ^C	16	18 ^C	20	22 ^C	24	28	32	36
Visit	1	2 ^{d}	3	4	5	6	7		8		9		10		11/EOT	12	13	14
EQ-5D-5L	x		x						x						x			x
Health resource utilization	x	x	x	Х	x	х	x		x		х		x		х	x	x	x
AE/SAE recording	x	x	x	Х	x	x	x		x		x		x		x	x	x	x
Optional assessments (for select	ct study sit	tes in Cana	da)															
Sputum and blood collection ^{bb}			x												x			x
Methacholine challenge ^{CC}			x												x			

ACQ=Asthma Control Questionnaire; ADA=anti-drug antibodies; AE=adverse event; AM=morning; ANA=anti-nuclear antibodies; AQLQ=Asthma Quality of Life Questionnaire; CXR=chest x-ray; ECG=electrocardiogram; DNA=deoxyribonucleic acid; ds=double-stranded; eDiary=electronic diary; EOT=end-of-study; FEF_{25-75%}=forced effective flow over the 25% to 75% range of the vital capacity; FeNO=fractional exhaled nitric oxide; FEV1=forced expiratory volume in 1 second; FVC=forced vital capacity; HADS=Hospital Anxiety and Depression scale; HbA1c=hemoglobin A1c; HIV=human immunodeficiency virus; ICS=inhaled corticosteroid; Ig=immunoglobulin; IMP=investigational medicinal product; IVRS=interactive voice response system; LABA=long-acting beta agonist; LAMA=long-acting muscarinic antagonist; LTRA=leukotriene receptor antagonist; OCS=oral corticosteroid; PEF=peak expiratory flow; PK=pharmacokinetics; PM=evening; q2w=once every 2 weeks; RNA=ribonucleic acid; Rnd=randomization; SAE=severe adverse event; SNOT-22=22-item Sino Nasal Outcomes Test.

- a The Screening period is from 3 to up to 8 weeks in duration (for patients who experience an asthma exacerbation that requires a change in OCS dose this period can be extended to 10 weeks to allow for 2 weeks of stabilization prior to randomization) to collect baseline data on asthma and to optimize the OCS dose. A follow up visit/s or call/s may be added during this visit depending upon the patient's response to changes in OCS dosing.
- b Randomization Visit (Visit 3) is defined as Day 1. Visit windows for subsequent visits are +/- 3 days.
- c Weeks 10, 14, 18, and 22 are scheduled as phone visits. Patients who are not (or whose caregivers are not) comfortable with self-administering the IMP will return to the study clinic for these visits.

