9.2.5 Systemic drug concentration and anti-drug antibodies

9.2.5.1 Sampling time

Blood samples of serum functional dupilumab and anti-dupilumab antibodies will be collected as designated in the study flow chart (Section 1.1). Patients who discontinue early from treatment or patients who choose not to roll over into a long-term study may be asked to return to the clinic to have additional ADA samples collected for analysis based on the overall clinical presentation at that time.

In the event of an SAE or any AESI of anaphylaxis or systemic allergic reaction related to IMP and requiring treatment, or severe injection site reaction lasting longer than 24 hours, samples will be collected near the onset and resolution of the event for any additional analysis if required or for archival purposes. An unscheduled systemic drug concentration page in the e-CRF must be completed as well.

Pre-existing anti-drug antibodies are defined as:

- An ADA positive response in the assay at baseline with all post treatment ADA results negative, OR
- An ADA positive response at baseline with all post treatment ADA responses less than 4-fold over baseline titer levels.

Treatment-emergent anti-drug antibodies are defined as:

- An ADA positive response in the assay post first dose, when baseline results are negative or missing.
- Treatment-boosted anti-drug antibodies are defined as:
- An ADA positive response in the assay post first dose that is greater-than or equal to 4-fold over baseline titer levels, when baseline results are positive.

Treatment-emergent (TE) ADA responses are further classified as Transient, Persistent or Indeterminate

- Persistent Response- defined as a treatment-emergent response with two or more consecutive ADA positive sampling time points, separated by more than 12-week period (with no ADA negative samples in between).
- Indeterminate Response- defined as a treatment-emergent response with only the last collected sample positive in the ADA assay
- Transient Response defined as a treatment-emergent response that is not considered persistent OR indeterminate

Unused samples collected for drug concentration or ADA analyses may be used for exploratory analyses.

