10 STUDY PROCEDURES

10.1 VISIT SCHEDULE

The clinical study consists of 3 periods:

- 1. Screening and OCS Optimization Period (from 3 to up to 8 weeks for those patients who experience an asthma exacerbation that requires a change in OCS dose this period can be extended to 10 weeks to allow for 2 weeks of stabilization prior to randomization; Visits 1 and 2)
- 2. Treatment Period (24 weeks): includes the randomization visit (Visit 3) and a 4-week induction phase (Visits 4 and 5), a 16-week OCS reduction phase (Visits 6-10), and a 4-week maintenance phase (Visit 11)
- 3. Post-treatment Period (12 weeks; Visits 12-14)

The study visits occur on the planned dates (relative to the first injection), as scheduled. After randomization, the visit schedule should be adhered to within the ± 3 day visit window.

Patients who permanently discontinue the study medication will be asked and encouraged to return to the clinic for all remaining study visits and participate in follow-up assessments according to the visit schedule. Under exceptional circumstances when a patient cannot come to the site for the scheduled visit/s, a phone contact can be made after sponsor approval is given. During the phone contact information about AEs, concomitant medications and exacerbation events should be collected.

Patients should be reminded that sexually active female patients of reproductive potential are required to practice effective contraception during the entire study duration, while taking dupilumab and for 12 weeks post last IMP dose.

Prior to all screening assessments, after discussion of participation in the study, the written consent form (including voluntary participation in pharmacogenetic testing/future use of blood samples) must be signed and dated.

Although the screening assessments for this study are grouped under the heading of 2 visits in this protocol, it is possible for them to be performed over more than the 2 scheduled site visits if necessary, as long as the screening window prior to randomization (Day 1) is respected. If certain dynamic laboratory tests do not meet the eligibility criteria, these laboratory assessments may be repeated, at the discretion of the Investigator, if it is judged to be likely to return to acceptable range for study inclusion within the screening visit window prior to Day 1. These patients do not need to sign a new ICF and be allocated a new patient number within this same screening window.

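### The threshold for a persistent ADA response (more than 84 days) equals the spacing of the ADA samples, so patients positive at two adjacent visits on schedule are labelled transient

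*SAP*

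**What the plan says.** SAP 2.1.6 divides treatment-emergent ADA responses (baseline negative or missing, positive after the first dose) into three classes.

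- **Persistent** needs "2 or more consecutive ADA-positive sampling time points separated by more than a 12-week period (84 days"), with no negative sample in between. Protocol 9.2.5.1 has the same strict threshold: "two or more consecutive ADA positive sampling time points, separated by more than 12-week period".
- **Indeterminate** means that the last sample collected is the only positive one.
- **Transient** takes everything left over: "Transient response is defined as a treatment-emergent response that is not considered persistent OR indeterminate".

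ADA status is determined "at Visits 3 (Week 0), 8 (Week 12), 11 (Week 24), and 14 (Week 36"). Table 10 in SAP 2.5.4 puts the three post-dose visits at Days 85, 169 and 253. Protocol 10.1 fixes the timing: "The study visits occur on the planned dates (relative to the first injection), as scheduled". Footnote b of the flow chart adds: "Visit windows for subsequent visits are +/- 3 days".

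Under SAP 1.4, patients who enter the extension study skip the post-treatment period and so have no Week 36 sample. Early discontinuers and patients who do not roll over "may be asked to return to the clinic to have additional ADA samples collected for analysis". After a serious adverse event or certain events of special interest, "samples will be collected near the onset and resolution of the event for any additional analysis if required or for archival purposes" (protocol 9.2.5.1).

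SAP 2.4.6.1.2 plans counts for each class and peak-titre summaries by class. It also allows the classes to be related to PK, efficacy and safety.

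**The concern.** The class is meant to separate a sustained antibody response from a passing one. A strict threshold of more than 84 days on a grid of exactly 84 days defeats that purpose for any patient whose run of positives covers just two adjacent visits. The clearest case is the roll-over patient positive at every scheduled post-dose sample. Nothing in that record suggests the response went away, yet the residual class calls it transient. A day or two of visit timing can reverse the label.

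At stake is how sustained responses are described. Persistence would be understated, and any exploratory comparison of persistent with transient responders would mix the two.

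**Working it through.** **1. The plan's own figure.** 12 weeks × 7 = 84 days, as SAP 2.1.6 states.

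**2. Scheduled gaps (Table 10 target days).** Week 12 to 24: 169 − 85 = 84. Week 24 to 36: 253 − 169 = 84. Week 12 to 36: 253 − 85 = 168.

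**3. The rules applied on schedule.** Baseline is negative or missing, and separation is taken from the first to the last positive of an unbroken run.

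| Week 12 | Week 24 | Week 36 | Run (days) | Label |
|---|---|---|---|---|
| + | + | none (roll-over) | 84 | transient |
| − | + | none (roll-over) | – | indeterminate |
| + | − | none (roll-over) | – | transient |
| − | + | + | 84 | transient |
| + | + | − | 84 | transient |
| + | + | + | 168 | persistent |

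The first and fourth rows are the problem. The run of 84 days is not more than 84, so the response is not persistent. There are two positives, so it is not indeterminate either. Yet it is still positive at the last sample taken.

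**4. Actual dates inside the windows.** Let *a* and *b* be the whole-day deviations at the earlier and later visit, each from −3 to +3. Visits are dated from the first injection, so gap = 84 + *b* − *a*.

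- Minimum 84 − 3 − 3 = 78; maximum 84 + 3 + 3 = 90.
- Transient when *b* ≤ *a*: 7 + 6 + 5 + 4 + 3 + 2 + 1 = 28 of 49 pairs (57%).
- Persistent when *b* > *a*: 6 + 5 + 4 + 3 + 2 + 1 = 21 of 49 pairs (43%).

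The percentages are probabilities only if the deviations are independent and uniform, which is an assumption. With Week 12 still uniform on ±3:

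- Week 24 uniform 0 to 3 days late: (4 + 3 + 2 + 1)/28 = 10/28 = 36% transient.
- Week 24 uniform 0 to 3 days early: (7 + 6 + 5 + 4)/28 = 22/28 = 79% transient.

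**5. Alternative thresholds.** At least 84 days makes the on-schedule pair persistent, but the 21 pairs with *b* < *a* (gaps of 78 to 83 days) stay transient. At least 78 days makes all 49 persistent.

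**6. How many patients (illustration).** The documents give no ADA incidence, roll-over share or visit-deviation data. Take 90 dupilumab patients, assume 2% to 10% positive at both Weeks 12 and 24, and 50% to 90% rolling over:

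- Both-positive roll-over patients: 90 × 0.02 × 0.5 = 0.9 to 90 × 0.10 × 0.9 = 8.1.
- Labelled transient: 0.9 × 10/28 = 0.3 to 8.1 × 22/28 = 6.4.

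This leaves out the Week 24/36 pattern. If the same 2% to 10% applied to non-roll-over patients for that pattern, the roll-over share drops out. The two patterns together would be 90 × 0.02 = 1.8 to 90 × 0.10 = 9.0 patients, with 1.8 × 10/28 = 0.6 to 9.0 × 22/28 = 7.1 labelled transient.

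**The case against.** The strongest reply is that nothing here is inconsistent. Protocol and SAP agree on a strict threshold, and transient is openly a residual class, so the label follows the rule. That is true: this is a rule that fits badly with its own sampling grid, and the two definitions do not contradict each other.

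The second reply is that little depends on it. Treatment-emergent incidence, which is the stated objective, does not use the class. By-visit ADA status and the listing of positive patients still show who was positive when, and the associations with efficacy and safety are optional. This stands too, and it sets the weight of the point.

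Third, the premise of a Week 12 sample is not secure everywhere. The flow chart and SAP 2.1.6 schedule one, but the Visit 8 procedure list in protocol 10.1.2.3.3 omits it. At a site that followed only that list, the Week 12/24 pattern could not arise from scheduled samples. This limits how often the first case occurs and needs reconciling in any event.

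Some stronger readings are tempting but unsupported:

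- *Every roll-over patient positive at both visits is called transient.* This is so on schedule or on nominal days. By actual date, a gap of 85 to 90 days gives persistent, and an event-triggered sample could change an individual label. SAP 2.1.6 does not say which dates apply.
- *The problem disappears for patients who reach Week 36, or once later data enter the report addendum.* A patient first positive at Week 24 and still positive at Week 36 is also 84 days apart on schedule and stays transient with complete data, unless an extra sample changes the label.
- *Baseline-positive patients are affected.* They are classed as pre-existing or treatment-boosted, outside this split.
- *Efficacy conclusions are at risk.* No efficacy test uses these classes.

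**Conclusion.** The point holds as a minor correction. On schedule, the rule gives a misleading label to two groups with negative or missing baseline ADA: roll-over patients positive at Weeks 12 and 24, and non-roll-over patients first positive at Week 24 and still positive at Week 36. Off schedule but inside the windows, timing decides the label.

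The arithmetic on gaps and offset pairs rests only on the documents. The 57%, 36% and 79% rest on assumed visit deviations, and the patient counts also on assumed ADA and roll-over rates. On those assumptions a handful of patients at most is involved. The consequence stays within the persistent and transient counts, their titre summaries and exploratory associations.

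**What to change.** **SAP 2.1.6, logged in the table of SAP 1.6.** Define persistent as a treatment-emergent response that is ADA-positive at two or more consecutive scheduled ADA visits, with no negative sample in between, and with the first and last positive samples at least 78 days apart by actual sampling date (84 days less the two 3-day windows).

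The minimum gap is needed because of the visit-based wording. If samples are assigned to visits by Table 10, the ADA windows for Visits 8 and 11 meet at Days 126 and 127, so off-schedule positives on, say, Days 120 and 130 would otherwise count as two consecutive visits. The present rule, based on the gap alone, does not have that weakness.

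Changing only to at least 84 days would be simpler and would settle the on-schedule case, but it leaves the label dependent on timing within the windows.

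**Protocol.** Align 9.2.5.1 at the next amendment; a separate one is not warranted, since any amendment needs ethics approval. Reconcile the Visit 8 procedure list in 10.1.2.3.3 with the flow chart and SAP 2.1.6 on the Week 12 ADA sample.

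**Cost.** One sentence and one table row in the SAP; no sample, visit or test changes. There are four downsides:

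- The 12-week criterion is relaxed by up to 6 days, so the persistent percentage rises and the transient percentage falls.
- Patients positive at Weeks 12 and 24 but negative at Week 36 become persistent in every in-window case. The present rule does this only from a gap of 85 days.
- Out-of-window visits less than 78 days apart are still missed.
- SAP and protocol definitions differ until the protocol is next amended.
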